10.1.2. Study Populations

The *Efficacy Population* will consist of those subjects meeting the study inclusion/exclusion criteria with no protocol violations judged to affect the ability to evaluate the subject whose DBT and FFDM images are diagnostically evaluable, and whose mammography images are available for the independent blinded evaluation regardless of the image quality. Non-available images will include:

- those lost due to corrupted media or inability of site to transport to image review center;
- subjects where no images are acquired.

The Sponsor will make any decisions regarding whether any subjects or any individual values belonging to a subject will be excluded from the evaluations when a protocol violation is considered to have a negative impact on the scientific aspects and interpretation of the study results. The reason(s) for any exclusion(s) will be documented in the study report.

The *Safety Population* will include all subjects enrolled into the study.

10.1.3. Subject Disposition and Characteristics

Subjects enrolled, imaged, and withdrawn will be summarized overall and by site and imaging modality. Descriptive statistics and summaries will be provided for demographics, medical histories, image acquisition, lesions and findings.

Specific subgroups of interest include stratification by the following variables:

- Age;
- Menopausal status; and
- Breast density.

10.1.4. Adverse Events

Adverse events will be reported from the time the subject enters the imaging suite for study procedures until the time the subject leaves the imaging suite after the study procedure. Device-related adverse events (AEs) and serious adverse events (SAEs) reported by subjects within 30 days of imaging (only those reported by subjects will be considered, and no separate 30-day follow-up is planned), and device malfunctions occurring in the safety population will be summarized with subject counts overall and by modality (DBT and FFDM). Additionally, individual subject listings will be provided to detail all AE/SAE information collected.

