5.3.3. Safety endpoint

Device-related adverse events (AEs), serious adverse events (SAEs), and device malfunctions by overall occurrence and imaging modality (DBT and FFDM) that occur during the study will be collected. No other clinical safety assessments will be performed.

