6.2. Study Timeframe

The study is expected to begin in the fourth quarter of 2014, and last for approximately two years (24 months), or until the target subject population is enrolled or the Sponsor otherwise indicates in writing that enrollment should be terminated. The end of the study shall be defined as the date when the last subject undergoes biopsy procedures and concordance is established, if applicable. Subject participation will be from the point of enrollment until truth determination of cancer status. The Investigator shall not begin the study until the applicable EC/IRB and necessary regulatory authority (when required) approval have been obtained.

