8.1. Digital Breast Tomosynthesis (DBT) and Full Field Digital Mammography (FFDM) Examinations

Prior screening and/or diagnostic FFDM and/or DBT images will be collected from each subject's medical record. If necessary (e.g. because prior screening and/or diagnostic FFDM and/or DBT

mammography images/views are not available or were not collected with GE equipment), a subject may undergo study-specific FFDM and/or DBT imaging. Study-specific imaging will include a bilateral two-view (both CC and MLO views) FFDM and/or DBT performed using the GE FFDM and/or DBT system available at the site and according to the hospital's standard procedure.

Two-view DBT and FFDM image acquisition (both CC and MLO views) shall be performed within 30 days of each other, regardless if FFDM or DBT was performed before or after the patient agreed to participate in the study. Subjects requiring study-specific imaging will undergo the following procedures:

- Enter a changing room to prepare for their mammogram;
- Each subject of child-bearing potential will wear a lead apron or have equivalent shielding during the FFDM and/or DBT procedures;
- Undergo FFDM and/or DBT procedure(s);
- Will be monitored for AEs and SAEs from study-specific DBT and FFDM and will be recorded in the source documents and CRF. Device malfunctions shall be sent to the Sponsor as per Section 12.5 Management of Device Complaints.

All scanning should be performed within the standard range of scan parameters, as per the manufacturer-provided operator's manual(s) for GE FFDM and DBT devices. The scan operator should conduct DBT and FFDM exam according to the standard clinical practice at the site with consideration for:

- Subjects with large breasts, because perspiration under the breast can cause the skin to soften, and become paper-thin;
- Any condition that exists which may cause unusual discomfort or tearing of the skin, which could include telling the subject the importance of correct positioning. The subject should be positioned carefully to avoid any discomfort to abnormalities such as warts, scarring, or skin which is not intact;
- Warmth of the front part of the breast support, which can be warm to the touch, as it contains electronic components that generate heat;
- Positioning the breast properly in FFDM and DBT in the CC position, where it is essential that the breast is lifted away from the chest wall and gently pulled forward, in order to visualize the maximum amount of breast tissue.

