12.3. Management of Adverse Event Reporting

Any adverse events will be recorded in the subjects study record and the Adverse Event Case Report Form. The following information should be obtained:

- Description of Event
- Date of onset and resolution
- Intensity (mild, moderate, severe)
 - **Mild:** Symptom(s) barely noticeable to the subject or does not make the subject uncomfortable. The AE does not influence performance or functioning. Prescription drugs are not ordinarily needed for relief of symptom(s).
 - **Moderate:** Symptom(s) of a sufficient severity to make the subject uncomfortable. Performance of daily activities is influenced. Treatment of symptom(s) may be needed.
 - **Severe:** Symptom(s) of a sufficient severity to cause the subject severe discomfort. Treatment for symptom(s) may be given.
- Serious (yes/no)
- Relationship to device (unrelated, possibly related, probably related)
 - **Unrelated:** The adverse event is reasonably expected to be related to (or caused by) a concurrent illness, effect of another device/drug or other cause, and is unlikely related to the investigational product
 - **Possibly related:** The adverse event is reasonably expected to be related to the investigational product, and an alternative etiology is equally or less likely compared to the potential relationship to investigational product
 - **Probably related:** There is a strong relationship to investigational product, or recurs on re-challenge, and another etiology is unlikely, or there is no other reasonable medical explanation for the event.
- Treatment given and/or action taken (procedure stopped, withdrawn from study, no action)

- Anticipated (yes/no)

Adverse events will be reported to the local EC/IRB per their policy.

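### The adverse-event reporting period is not reconciled across sections, and after the woman leaves the imaging suite only events she reports count, so later imaging-related events may be under-counted

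*Combined protocol and SAP*

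**What the plan says.** Five places in the combined protocol and SAP bear on when an AE counts.

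- **10.1.4, first sentence,** which confines reporting to her time in the suite: "Adverse events will be reported from the time the subject enters the imaging suite for study procedures until the time the subject leaves".
- **10.1.4, second sentence:** the summary covers "Device-related adverse events (AEs) and serious adverse events (SAEs) reported by subjects within 30 days of imaging", with the qualification that "only those reported by subjects will be considered, and no separate 30-day follow-up is planned".
- **Synopsis and 5.3.3:** the safety endpoint is device-related AEs, SAEs and device malfunctions "that occur during the study will be collected. No other clinical safety assessments will be performed". Under 6.2, "Subject participation will be from the point of enrollment until truth determination of cancer status".
- **8.1:** for women having study-specific imaging, "Will be monitored for AEs and SAEs from study-specific DBT and FFDM and will be recorded in the source documents and CRF". No period is given.
- **12.3:** "Any adverse events will be recorded in the subjects study record and the Adverse Event Case Report Form". No period is given here either. The definition in 12.2 includes events unrelated to the device, and the causality scale in 12.3 has an unrelated category.

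Section 12.1 lists bruising, discomfort and skin injury as expected events, without saying when they appear. Section 8.4 requires no further appointment after a positive biopsy or documented concordance. No section specifies an AE enquiry at the biopsy visit.

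**The concern.** Safety is a named endpoint, and 5.3.3 rules out any other clinical safety assessment, so these counts are all the safety information the study yields. With up to three sites, a site following 12.3, one following 5.3.3 and one following the first sentence of 10.1.4 would record different sets of events. The difference could then be taken for a difference between sites.

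A second issue lies in the words that limit the 30-day summary to events reported by subjects. After suite exit the plan waits for the woman to report. Taken literally, it also sets aside an event that site staff observe but she does not mention. Both features can only lower the count. Because the data are meant to support a labelling submission (synopsis and 15.1), a low count should not be open to reading as a complete one.

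**Working it through.** The plan states no AE rate, no safety sample size and no safety comparison, so there is no figure to reproduce. The check is to pass the same event through each section.

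1. **Bruise on day 2, attributed to imaging.** Outside the first sentence of 10.1.4. Inside the second if she reports it. Inside 5.3.3 if truth is not yet determined. Recordable under 12.3.
2. **Skin tear seen by staff on day 5 and not mentioned by the woman.** Recordable under 12.3, and inside 5.3.3 if truth is pending. Left out of the 10.1.4 summary on a literal reading.
3. **Device-related event on day 20, reported, after truth determination.** Inside 10.1.4. Outside her participation as 6.2 defines it.
4. **Device-related event on day 40, truth still pending.** Inside 5.3.3. Outside the 30 days of 10.1.4.
5. **Non-serious biopsy complication.** Not related to the imaging device, so outside 5.3.3 and outside the 30-day summary, but an AE under 12.2 and 12.3. If serious, its place in 5.3.3 depends on whether device-related also qualifies the SAEs, which the sentence leaves unclear. Section 12.4 requires all SAEs to be reported, with no window.

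Cases 3 and 4 show that the 5.3.3 period can be shorter or longer than 30 days, since truth determination has no fixed day. If the phrase in 5.3.3 is instead taken to mean the calendar study, the period would vary with enrollment date, which does not help.

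**Direction of the effect.** Let d be the share of device-related events that arise after suite exit, and s the probability that such an event is reported by the woman within 30 days. With full capture in the suite,

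captured share = 1 − d(1 − s).

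Both d and s are assumptions; the documents give neither. For s from 0 to 0.75:

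- d = 0.1: 1 − 0.1 × 1 = 90%, up to 1 − 0.1 × 0.25 = 97.5%
- d = 0.5: 1 − 0.5 × 1 = 50%, up to 1 − 0.5 × 0.25 = 87.5%
- d = 0.8: 1 − 0.8 × 1 = 20%, up to 1 − 0.8 × 0.25 = 80%

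Capture is complete only if d = 0 or s = 1. The direction is therefore settled by the design. The size is not: the range runs from trivial to large according to values the documents do not supply.

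**Is there a contact at which to ask?** Exclusion criterion 2 (7.6) bars diagnostic or surgical breast intervention before study-related imaging, so the biopsy follows imaging. Women who do not complete biopsy are withdrawn (8.3), and 8.6.1 calls for a final evaluation at withdrawal.

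**The case against.** The strongest reply is that 10.1.4 is coherent as it stands. Its two sentences can be read as two tiers: every AE in the suite, then device-related AEs and SAEs that subjects report to 30 days. Section 12.3 lists data items and sets no competing window, while 8.1 ties monitoring to study-specific imaging. Passive capture is openly disclosed. The systems are commercially available, no hypothesis is tested (5.1), and success depends on accrual alone (10.4). An answer to a site's question would also be reported by the subject, and the CRF is not in the documents, so prompting cannot be ruled out.

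Much of this stands. A reader might infer that the two sentences of 10.1.4 contradict each other outright. The two-tier reading is available, so that goes too far, although the text does not state the tiers. The silence of 12.3 is a missing cross-reference rather than a rival window.

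The reply does not reach two things. The two-tier reading leaves the synopsis and 5.3.3, which end at an unfixed date, unreconciled with 30 days. It also leaves the staff-observed event excluded by the literal wording. Whether or not the CRF prompts, the protocol specifies no enquiry after suite exit.

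**Conclusion.** The point holds as a limited one. The reporting period is not reconciled across the synopsis, 5.3.3, 8.1, 10.1.4 and 12.3, and this needs no assumption. Post-suite capture is passive and limited to subject-reported events, so imaging-related events arising after exit, including any that staff observe, may be under-counted.

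A reader might go further and infer that delayed bruising will be under-counted, or put a number on it. For instance, if 30% to 70% of post-suite events were reported, their rate would be understated by 1/0.7 = 1.4-fold to 1/0.3 = 3.3-fold. The documents do not support either step. Section 12.1 gives no onset times, no event or reporting rate appears anywhere, and the fold figure merely restates the assumed reporting share for post-suite events. The size is not derivable.

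The consequence is confined to a descriptive safety summary. It does not touch the accrual target or the later reader comparison. The change is worth making because safety is a named endpoint and the remedy is cheap.

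**What to change.** - **State 10.1.4 as two tiers:** all AEs while the woman is in the suite for study procedures, and device-related AEs and SAEs to 30 days after study-specific imaging. Align the synopsis, 5.3.3, 8.1 and 12.3 to it, and say whether device-related qualifies SAEs in the endpoint.
- **Delete the restriction to subject-reported events,** so that events site staff observe or learn of within the period are counted.
- **Add one CRF question** on imaging-related events at the biopsy visit, or at the final evaluation for withdrawn subjects. This should supplement the 30 days and not replace them: biopsy may follow imaging closely, and closing the window there could shorten it.
- **Record biopsy-related events separately** from events related to the imaging devices.
- **In the study report,** describe events arising after that contact as passively reported and their count as a lower bound.

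The cost is wording in five places and one more CRF item at an existing contact. The small downside is that a few more minor AEs will be recorded.

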| Clinical (human) |  | Initially Asymptomatic Women Referred for Breast Biopsy |
| Pre-Clinical (animal) |  | |
| External Bench |  | |

¹ Subjects who had screening DBT or screening/diagnostic FFDM imaging on non-GE equipment may be enrolled if they agree to undergo repeat imaging on a GE system; If the prior screening and diagnostic DBT or mammographic examinations were not conducted at the recruiting site, review of those images by the investigator must confirm that breast biopsy recommendation is warranted and GE access to the images in DICOM digital format must be granted.

² Screening FFDM and DBT image acquisitions must be within 30 days of each other.

Brief Description of Study Purpose: This study is being conducted to accrue cancer cases for a subsequent blinded reader study comparing the diagnostic accuracy and performance of digital breast tomosynthesis (DBT) performed with the GE SenoClaire® GE Digital Breast Tomosynthesis compared to conventional GE full-field digital mammography (FFDM) in asymptomatic women. The study also provides for exploratory analysis of cancerous and non-cancerous lesion characteristics detected by DBT and FFDM systems. This statistically powered study is being conducted to support regulatory claims to expand the labeling of the DBT system.
	

Sponsor Name: GE Healthcare (GEHC) Sponsor contact: [name], Senior Clinical Affairs Project Manager III
	
Address: [name] US [contact] E-mail: [contact]

Device/Product GEHC Modality: Detection and Guidance Solutions (DGS) Device/Product GEHC Class: SenoClaire® - GE Breast Tomosynthesis
	

Device/Product Description: Commercially available SenoClaire® - GE Breast Tomosynthesis is a Digital Breast Tomosynthesis (DBT) device available for commercial full-field digital (FFDM) mammography systems (GE Senographe® Essential Full-Field Digital Mammography) and read on IDI MammoWorkstation with Volume-Preview Synthetic 2-D Mammography (V-Preview).
	

Regulatory Status: Pre-Market  Post-Market  DBT, FFDM, and IDI MammoWorkstations used in this study are considered post-market in the US and Europe. V-Preview for DBT is a commercially available tool on the IDI MammoWorkstation not currently indicated for breast cancer diagnosis use.
	

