4.1. Risk Category and Rationale (US Only)

The SenoClaire® - GE Breast Tomosynthesis (DBT) and mammography devices under investigation are considered non-significant risk devices per the 21 CFR 812. 3 definition:

- 1) it is not intended as an implant;
- 2) it is not purported or represented to be for a use in supporting or sustaining human life;
- 3) it is not for a use of substantial importance in diagnosing, curing, mitigating, or treating disease, or otherwise preventing impairment of human health;
- 4) and it does not otherwise present a potential for serious risk to the health, safety, or welfare of a subject.

This designation of non-significant risk is supported by the study design in which DBT data will not be used as the sole measure of diagnosis without distinct confirmation from conventional methods, such as mammography or other standard of care procedures (e.g., breast ultrasound, breast magnetic resonance imaging (MRI), or biopsy) at the investigational site.

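### Can device-related adverse events be counted by modality when the listed AE items hold one causality rating and no modality item?

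*Combined protocol and SAP*

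**What the plan says.** Section 5.3.3 sets the only safety endpoint: device-related AEs, SAEs and "device malfunctions by overall occurrence and imaging modality (DBT and FFDM) that occur during the study will be collected". Section 10.1.4 turns this into a table in which events "will be summarized with subject counts overall and by modality (DBT and FFDM"), with individual listings. It counts device-related events that women report within 30 days of imaging.

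Section 12.3 introduces the content of the AE record with "The following information should be obtained". The items are description, onset and resolution dates, intensity, seriousness, "Relationship to device (unrelated, possibly related, probably related"), treatment or action, and whether the event was anticipated. The Unrelated category takes in events due to a concurrent illness or the "effect of another device/drug or other cause, and is unlikely related to the investigational product".

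The product is not defined there. The synopsis lists "Device/Product GEHC Class: SenoClaire", whereas Section 4.1 speaks of the DBT "and mammography devices under investigation are considered non-significant risk devices".

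Section 8.1 uses images already on record where they qualify, adds study-specific exams only where needed, and limits the gap between the two modalities to 30 days. AE monitoring there is attached to the study-specific exams.

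**The concern.** The planned table needs each related event to be assigned to DBT, FFDM or both. The items in Section 12.3 do not record that assignment, and no rule supplies it.

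Two readings of the product give different trouble. If it means SenoClaire alone, an event caused by FFDM is the effect of another device, is rated Unrelated, and never reaches the FFDM row. If it means both devices, a related rating does not say which one. Timing need not help, because the two 30-day windows can overlap. Nor does event type, because Section 12.1 expects no DBT side effects beyond those of conventional mammography.

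At stake is the by-modality part of the safety endpoint in a study "being conducted to support regulatory claims to expand the labeling of the DBT system". Two analysts could fill the DBT and FFDM rows differently from the same events.

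**Working it through.** The plan gives no AE rate or expected count, so there is no figure of its own to reproduce. Two checks are possible.

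**1. How far do the windows overlap?** Inputs: gap d between exams, 0 to 30 days (Section 8.1); event window of 30 days after imaging (Section 10.1.4).

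- Days inside both windows = 30 − d.
- Days covered by at least one window = 30 + d.
- Share of covered time that is ambiguous = (30 − d)/(30 + d).

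| d (days) | Overlap (days) | Covered (days) | Ambiguous share |
|---|---|---|---|
| 0 | 30 | 30 | 100% |
| 7 | 23 | 37 | 62.2% |
| 14 | 16 | 44 | 36.4% |
| 21 | 9 | 51 | 17.6% |
| 29 | 1 | 59 | 1.7% |
| 30 | 0 | 60 | 0% |

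Only same-day exams leave no date that separates the modalities. For any longer gap, an onset before the second exam, or more than 30 days after the first, falls in one window only. The recorded onset date places it.

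The table applies only when both exams start a window. Monitoring in Section 8.1 is tied to study-specific exams, and Section 10.1.4 opens with study procedures. On that reading, a woman with one study-specific exam has one window, and a monitored event belongs to that exam. Section 12.1 treats repeating both modalities as the conditional case (about four times the usual dose, against about twice otherwise). If imaging on record also starts a window, the overlap reaches every pair less than 30 days apart; Section 10.1.4 does not say which is meant.

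**2. How much could the rows move?** Let k women each have one related event in the overlap. A related event must enter at least one row, because Section 10.1.4 gives no ground for dropping it.

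- All to DBT: rows (k, 0). All to FFDM: rows (0, k). All to both: rows (k, k).
- Each row therefore runs from 0 to k, and the two rows sum to between k and 2k, against an overall count of k.
- For an assumed k of 5: each row 0 to 5, sum 5 to 10, overall 5.

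The overall count does not depend on the allocation. The documents give neither k nor the share of women with two study-specific exams.

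**Which reading of the product fits?** Taking it as SenoClaire alone would defeat Sections 5.3.3 and 10.1.4, which both call for FFDM counts. It would also conflict with Section 8.1, which monitors events from FFDM; Section 12.1, which lists expected events for digital mammography on the Senographe Essential; and Section 4.1, which puts both devices under investigation. The rated item itself refers to the device. Reading it as both devices fits all of these.

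**The case for a change.** The best case for a change does not rest on overlapping windows. The causality rating is the filter that admits an event to the table. A site that took the product to be SenoClaire would rate an FFDM-caused event Unrelated, even in a woman whose only study-specific exam was FFDM. The event would then drop out of the overall device-related count as well as the FFDM row. For same-day exams Section 12.3 asks for a date and not a time. DBT is an add-on to the same Senographe unit (Section 3.1), so a unit's serial number need not separate the two. Section 10.3 analyzes data as collected, so an attribution not recorded has no planned recovery. The remedy would be a definition, a form field and an allocation rule.

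Part of this stands: the product is undefined, and nothing says how to count an event that could belong to either exam. But the narrow reading goes against the endpoint and several other sections. Section 12.3 does not present its list as exhaustive, and neither the AE form nor the SAE form is in the documents, so a modality field cannot be ruled out. Free text may name the exam. Section 15.3 provides a clarification form for gaps in the record. As for denominators, Section 10.1.3 already summarizes women imaged by modality; splitting study-specific from record imaging would be a refinement.

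**Conclusion.** No change follows. What remains is an unwritten definition and an unwritten counting rule for one descriptive table. A sponsor who has committed to collecting events by modality and monitoring each study-specific exam would take both devices as the product and show any inseparable event as such. The individual listings would let a reader see each case.

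The ambiguity is limited mainly to women with both exams done as study procedures and an onset within 30 days of both: 30 − d days, complete only at d = 0. Its size in events is unknown. Nothing inferential depends on it: Section 5.1 tests no hypothesis, Section 10.4 defines success by accrual, and the accuracy comparison belongs to ADAPT-BIE.

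This rests on two assumptions: that the product covers both devices, and that study-specific imaging starts the 30-day window. If any imaging starts it, more women fall in the overlap, but the effect still stays within the by-modality rows. Device malfunctions are left out, because Section 12.5 was not available for review.
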